4.7.2 Secondary Efficacy Endpoints

4.7.2.1 Overall Survival

1) Definition:

- Observation period: For all subjects, the time from randomization to OS-cutoff date. The OS-cutoff date was set as the date after 728 days (2 years) from the day that the last subject started IMP administration without consideration of withdrawal by the OS-cutoff date.

- Definition: The time from randomization until death from any cause by the OS-cutoff date.
- Event: Death from any cause by the OS-cutoff date.
- Censoring: If an event has not been observed by the OS-cutoff date, then the last confirmed survival date will be used as the censoring date.

2) Analysis Set:

FAS, PPS

3) Analysis Method:

The same analysis will be conducted as for DFS.

4.7.2.2 Quality of Life

1) Based on the scoring rule (EORTC QLQ-C30 version 3), the following scales and single items will be calculated and analyzed.

Table 4.7.2.2-1	Quality of Life Scale
Global health status / QOL	
Functional Scale: Physical, Role, Cognitive, Emotional, Social	
Symptom Scale: Fatigue, Pain, Nausea/Vomiting	
Single Items: Dyspnea, Sleep disturbance, Appetite loss, Constipation, Diarrhea, Financial impact	

Scoring rule¹³:

The QLQ-C30 is composed of both multi-item scales and single-item measures. These include 5 functional scales, 3 symptom scales, a global health status/QOL scale, and 6 single items. Each of the multi-item scales includes a different set of items - no item occurs in more than one scale.

- All of the scales and single-item measures range in score from 0 to 100.
- A high scale score represents a higher response level. Thus a high score for a functional scale represents a high/healthy level of functioning, a high score for the global health status/QOL represents a high QOL, but a high score for a symptom scale/item represents a high level of symptomatology/problems.

Scoring principle:

- 1) Estimate the average of the items that contribute to the scale; this is the raw score (RS).

- 2) Use a linear transformation to standardize the RS, so that scores range from 0 to 100; a higher score represents a higher ("better") level of functioning, or a higher ("worse") level of symptoms

Technical summary:

In practical terms, if items I_1, I_2, \dots, I_n are included in a scale, the procedure is as follows:

Raw score (RS)

Calculate the RS:

$$\text{Raw score} = \text{RS} = \frac{I_1 + I_2 + \dots + I_n}{n}$$

Linear transformation

Apply the linear transformation to 0-100 to obtain the score S

$$\text{Functional scales: } S = \left\{ 1 - \frac{(RS - 1)}{\text{Range}} \right\} \times 100$$

$$\text{Symptom scales / items: } S = \left\{ \frac{(RS - 1)}{\text{Range}} \right\} \times 100$$

$$\text{Global health status / QOL: } S = \left\{ \frac{(RS - 1)}{\text{Range}} \right\} \times 100$$

- Range is the difference between the maximum possible value of RS and the minimum possible value. The QLQ-C30 has been designed so that all items in any scale take the same range of values. Therefore, the range of RS equals the range of the item values. Most items are scored 1 to 4, giving range = 3.
- The exceptions are the items contributing to the global health status/QOL, which are 7-point questions with range = 6, and the initial yes/no items on the earlier versions of the QLQ-C30 which have range = 1.

2) Analysis Set:

FAS, PPS

3) Analysis Method:

- A summary of descriptive statistics of each score will be calculated by treatment arm.

- Mixed-effect model repeated measures (MMRM) will be performed with treatment as fixed effect.
 - The dependent variable is the change from baseline to each visit in each scale of QOL score. The model will include treatment arm, protocol-specified visit, and treatment-by-visit interaction.
 - Changes from baseline at each time point will be plotted in trend diagrams. The difference of Least square (LS)-means and CI between two treatment arms will also be generated.
- The primary hypothesis test is the test of the difference of LS-means between treatment arms over time.

- The mixed model is as follows:

$$Y = X\beta + Zu + \varepsilon$$

- A key assumption is that u and ε are normally distributed with

$$E \begin{bmatrix} u \\ \varepsilon \end{bmatrix} = \begin{bmatrix} 0 \\ 0 \end{bmatrix} \quad \text{and} \quad \text{Var} \begin{bmatrix} u \\ \varepsilon \end{bmatrix} = \begin{bmatrix} G & 0 \\ 0 & R \end{bmatrix}$$

- The mean will be modeled as $E[Y] = X\beta$ and the variance will be modeled as $\text{Var}[Y] = ZGZ' + R$. Therefore, the variance of Y can be modeled by setting up the structure of G and R.
- The covariance structure will be assumed to be UN. It could be switched from UN to TOEP (Toeplitz), CSH (Heterogeneous Compound Symmetry), AR(1) [(Autoregressive(1)], CS (Compound Symmetry) and VC (Variance Components) in this order if convergence is not achieved.
- Restricted maximum likelihood (REML) will be used to make the inference.
- All analyses will be performed on the observed data.
- Discontinuation assessment will be analyzed using the following allowance window.
If two values fall into the same visit window, then the latter will be taken into analysis.

Week	Target Day ^a	Study Day Interval ^a		
1(Baseline)	1	-7	-	1
5	29	2	-	43
9	57	44	-	71
13	85	72	-	99
17	113	100	-	127
21	141	128	-	155
25	169	156	-	183
29	197	184	-	211

33	225	212	-	239
37	253	240	-	267
41	281	268	-	295
45	309	296	-	323
49	337	324	-	351
53	365	352	-	379
57	393	380	-	407
61	421	408	-	435
65	449	436	-	463
69	477	464	-	491
73	505	492	-	519
77	533	520	-	547
81	561	548	-	575
85	589	576	-	603
89	617	604	-	631
93	645	632	-	659
97	673	660	-	687
101	701	688	-	715
105	729	716	-	743

a. Relative to the first day of IMP taken in treatment phase (Date of first IMP taken is defined as the Day 1)

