6.3 Method of Minimizing or Avoiding Bias

The treatment allocation code will be double-blinded during the treatment period, meaning neither the investigator nor the subject will know whether the treatment administered is OCV-501 or placebo. The sponsor's trial personnel, such as those involved in monitoring, data management, and data analysis, including personnel belonging to contract research organizations (CROs), will not have access to the treatment allocation code during the conduct of the trial. Only the subject randomization center will have access to the treatment allocation code for this trial, and only if it is needed in an emergency.

OCV-501 vials and placebo vials will be indistinguishable in appearance and shape.

Blinding is critical to the integrity of this trial. However, in the event that a subject experiences a medical emergency in which knowledge of the IMP is critical to the subject's management, the blind may be broken by the investigator. The need to break the blind must first be discussed with the sponsor and the best method to do this will be determined. The treatment allocation code should be kept confidential and revealed only to those individuals that must be informed for medical management of the subject. See Section 8.2.4 for procedural details.

For measurement of the OCV-501-specific IFN- γ production, WT1-killer peptide specific IFN- γ production, anti-OCV-501 antibody level, and anti-WT1 antibody level, the results will not be revealed until unblinding at conclusion of the trial. If a medical emergency occurs in a subject and knowledge of his or her IMP randomization code is considered important for treatment, the emergency code will be broken according to Section 8.2.4, [Emergency Code Breaking \(Procedure for Unblinding During the Trial Period\)](#).

The randomization will be stratified by two stratification factors: country/region (Japan, Republic of Korea, Taiwan), and age at the time of providing informed consent (60 to 64 years, 65 to 70 years, and ≥ 71 years) to minimize imbalances between the treatment arms.

7 Trial Procedures

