7.1.3.1.1 Week 1 (1st Administration [Day 1])

The following observations, examinations, evaluations, and IMP administration will be performed. The date and results of observations, examinations, and evaluations, and the date of blood samplings will be recorded in the medical records and CRF.

- 1) A medical interview by investigator or subinvestigator will be performed before IMP administration.
- 2) Blood sampling for HLA genotyping (HLA-DRB1, HLA-DRB3, HLA-DRB4, HLA-DRB5, HLA-DPB1, HLA-DQB1, and HLA-A) will be performed.
- 3) Adverse event observation and a concomitant drug survey will be performed.
- 4) Subjects will receive the IMP (3 mg of OCV-501 [0.4 mL] or placebo [0.4 mL]) according to the IMP pack number (unique ID No.) provided through the IVRS or the IWRS at each scheduled visit. The IMP pack number (unique ID No.) will be issued according to the treatment allocation code. The IMP will be subcutaneously administered at the axilla or inguinal region.
(The subject's general conditions, including injection site reaction, must be observed at the trial site for one hour after IMP administration.)
- 5) Blood sampling for measurement of WT1 mRNA expression level will be performed before IMP administration.
- 6) QOL (EORTC QLQ-C30) self-assessment will be performed by subjects.

- 7) Blood sampling for measurement of OCV-501-specific IFN- γ production, WT1-killer peptide specific IFN- γ production, anti OCV-501 antibody level, anti-WT1 antibody, and immunoglobulin will be performed before IMP administration will be performed.

If the following examinations were conducted within 7 days before IMP administration, the data can be used as the Day 1 examination data.

- 8) Body weight measurement will be performed before IMP administration.
- 9) Measurement of vital signs will be measured before IMP administration (blood pressure, pulse, and body temperature).
- 10) Blood sampling for a hematology test will be performed before IMP administration.
- 11) Peripheral blood smear preparation will be performed.
- 12) Blood sampling for a blood biochemistry test will be performed before IMP administration.
- 13) Performance status (ECOG PS) will be measured.
- 14) A urine sample for urinalysis will be collected before IMP administration.

7.1.3.1.2 Weeks 2, Week 4, Week 6, and Week 8

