 - In the model of Cox analysis, treatments effect will be adjusted with covariates (Age, Country/Region and WT1 mRNA level at Day 1). The model with covariates (WT1 mRNA only) or model without covariates will be also analyzed. In these models, age will be categorized into 3 groups (60 to 64 years, 65 to 70 years, ≥ 71 years), Country/Region into 2 groups (Japan, Republic of Korea+Taiwan), WT1 mRNA into 4 groups (<50, 50-199, 200<= and Unknown).
 - BRESLOW method will be used for ties.
 - Proportionality assumption in Cox proportional hazard model will be assessed using 2 methods:
 - 1) SAS PHREG procedure ASSESS PH option will be used for checking proportional hazard assumption.
 - 2) Look at the log-minus-log survival plots graphically. If the graph results in parallel lines then the proportionality assumption is satisfied.
- HR and its 95% CI at every 3 months interval will be calculated by adding a time varying covariate to Cox Proportional Hazards model as an alternative analysis if the proportionality assumption fails. The model will be as follows:

$$\lambda(t;X) = \lambda_0(t) \exp(\beta_1 \text{trt} * \text{period}_1 + \beta_2 \text{trt} * \text{period}_2 + \dots)$$

where $\lambda_0(t)$ is the baseline hazard function,

trt is the treatment arm(1= OCV-501 and 0= Placebo) and

$$period_1 = \begin{cases} 1 & \text{if } 0 \leq DFS \text{ time} < 3 \text{ Months} \\ 0 & \text{otherwise} \end{cases}$$

$$period_2 = \begin{cases} 1 & \text{if } 3 \leq DFS \text{ time} < 6 \text{ Months} \\ 0 & \text{otherwise} \end{cases}$$

...

So HR (OCV-501 vs. Placebo) for each period will be calculated as follows:

$$\lambda(\text{OCV-501}|\text{period}_k) = \lambda_0(t)\exp(\beta_k)$$

$$\lambda(\text{Placebo}|\text{period}_k) = \lambda_0(t)$$

$$\text{HR}(\text{OCV-501 vs. placebo}|\text{period}_k) = \lambda_0(t)\exp(\beta_k) / \lambda_0(t) = \exp(\beta_k)$$

$$95\% \text{ CI} : [\exp(\beta_k - 1.96 * \sqrt{\text{Var}(\beta_k)}), \exp(\beta_k + 1.96 * \sqrt{\text{Var}(\beta_k)})]$$

- For exploratory purposes, the incidence rate over the entire follow-up period will be calculated using the person-year method by treatment arm as follows.

- 1) Calculate the number of events and person-year at risk by treatment arm.
- 2) Calculate the incidence rates and its corresponding 95% CI by treatment arm. (1 year is calculated as 365.25 days)

$$\text{Rate} = \frac{\text{Number of events}}{\text{Person - year}}$$

95% CI:

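### The QOL repeated-measures model omits the Day 1 score and the stratification factors, so the arm comparison is less precise than the collected data allow

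*SAP*

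**What the plan says.** SAP 4.7.2.2 sets up a mixed model for repeated measures for every QLQ-C30 scale. On the outcome: "The dependent variable is the change from baseline to each visit in each scale of QOL score". On the fixed effects: "The model will include treatment arm, protocol-specified visit, and treatment-by-visit interaction". On the test: "The primary hypothesis test is the test of the difference of LS-means between treatment arms over time". On covariance: "The covariance structure will be assumed to be UN", with a sequence of simpler structures ending in "CS (Compound Symmetry) and VC (Variance Components) in this order if convergence is not achieved".

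Nothing elsewhere adds a term. The table of changes in SAP 4.13 records only that a mixed model will be used for QOL. Protocol 11.3.1.2 calls the QOL least squares means adjusted means but does not say what they are adjusted for.

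The candidate covariates are all available:

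- **Day 1 score.** Protocol 7.1.3.1.1 has, at Week 1: "QOL (EORTC QLQ-C30) self-assessment will be performed by subjects".
- **Strata.** Protocol 6.3: "The randomization will be stratified by two stratification factors", namely country/region and age group.
- **Already used elsewhere.** In the SAP 4.7.1.1 Cox model for DFS, which SAP 4.7.2.1 carries over to OS, "treatments effect will be adjusted with covariates (Age, Country/Region and WT1 mRNA level at Day 1". That model groups region as Japan against Republic of Korea plus Taiwan.

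**The concern.** Subtracting the Day 1 score is not the same as adjusting for it. A change score fixes the slope on baseline at 1. Unless the correlation between baseline and follow-up is perfect, that slope is too steep, and the excess baseline noise goes into the residual. Every change from one subject carries the same Day 1 error, so averaging over visits does not remove it. The loss is therefore greatest for a comparison pooled over time.

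QOL is a stated secondary objective. At most 120 subjects are planned, and most are expected to relapse or die within two years. Intervals that are wider than necessary can hide or blur a QOL difference. A chance Day 1 imbalance would also remain uncorrected.

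There is a smaller point on covariance. If variance components is applied to the residual matrix with no random subject effect, it treats a subject's changes as independent although they share one baseline. It is the last of six structures and unlikely to be reached.

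**Working it through.** The documents state no QOL power, standard deviation, effect size or correlation, so there is no QOL figure to reproduce.

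**Inputs from the documents**

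- 60 subjects per arm (Protocol 3.4).
- 26 post-baseline analysis windows, Week 5 to Week 105 every 4 weeks (SAP 4.7.2.2 window table).
- Exponential DFS, with 2-year rates of 20% on placebo and 35% to 40% on OCV-501 (SAP 4.12).

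**Assumed.** Equal variance at all visits (SD = 1), the same correlation ρ between any two visits, ρ from 0.4 to 0.8, and QOL observed until relapse or death.

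**Residual covariance per subject** (I = identity, J = matrix of ones)

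- Change score, as planned: (1−ρ)(I + J). The single-visit variance is 2(1−ρ).
- Change score adjusted for baseline: (1−ρ)(I + ρJ). The single-visit variance is 1−ρ².

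**Complete data**

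- One visit: ratio adjusted/planned = (1−ρ²)/[2(1−ρ)] = (1+ρ)/2. This is 0.70 at ρ = 0.4 and 0.90 at ρ = 0.8, so the variance is cut by 30% to 10%.
- Average over m visits: ratio = (ρ + 1/m)/(1 + 1/m). With m = 26 this is 0.422 at ρ = 0.4, 0.711 at 0.7 and 0.807 at 0.8, so the cuts are 58%, 29% and 19%.

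Both ratios are below 1 for every ρ below 1.

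**With dropout following DFS (20% against 35%).** This uses generalised least squares information with the covariance known. The arm difference is averaged equally over the 26 visits, in SD units:

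| ρ | SE planned | SE adjusted | variance cut | SE cut |
|---|---|---|---|---|
| 0.4 | 0.1577 | 0.1081 | 53% | 31% |
| 0.5 | 0.1440 | 0.1078 | 44% | 25% |
| 0.6 | 0.1288 | 0.1038 | 35% | 19% |
| 0.7 | 0.1115 | 0.0958 | 26% | 14% |
| 0.8 | 0.0911 | 0.0827 | 17% | 9% |

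The 95% half-width is 1.96 × SE. At ρ = 0.4 it goes from 0.31 to 0.21 SD, and at ρ = 0.7 from 0.22 to 0.19 SD. With OCV-501 DFS at 40%, each variance cut moves by less than 1 point.

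**Single visits, same dropout, ρ = 0.4 to 0.8.** The variance cut is 30% to 10% at Week 5, 21% to 7% at Week 53 and 13% to 4% at Week 105. It shrinks because the mixed model already borrows from earlier visits.

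**Sensitivity**

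- *Dropout.* With an assumed 4% dropout per visit instead, the over-time SE falls by 25.2% at ρ = 0.5 and 13.7% at ρ = 0.7.
- *Correlation pattern.* With an assumed first-order autoregressive pattern (adjacent-visit correlation 0.90, 0.95, 0.98), the over-time variance cut is 50%, 33% and 16%. The Week 5 gain is then only 5% to 1%, and the Week 105 gain 34% to 16%.
- *Finite samples.* In 500 simulated trials per ρ, baseline alone cut the over-time variance by 51% (0.4), 24% (0.7) and 17% (0.8). Adding age and region as pure noise gave 50%, 23% and 15%.

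**Age and region.** If they explain a share R² of the residual variance, the SE falls by about 1−√(1−R²): 0% at R² = 0, 2.5% at 0.05 and 5.1% at 0.10. The documents give no R².

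**The case against.** The omission is not in dispute. The case against concerns its size and the remedy.

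- **Meaning of the test.** The SAP's phrase could mean visit-wise differences or an arm-by-visit pattern rather than an average. For the Week 5 to Week 53 change in the arm difference, the variance cut is only 1.1% to 0.3% (ρ = 0.4 to 0.8), because the shared baseline nearly cancels. The arithmetic stands, but an interaction contrast is not the natural reading of a difference in least squares means between arms over time. Under the visit-wise reading the smaller single-visit gains apply.
- **Cost of baseline-by-visit.** It adds 25 parameters to a model whose unstructured matrix already has 26 × 27/2 = 351. In 200 simulated trials per ρ, the term left the over-time gain unchanged (52% with and without it at ρ = 0.4). It reduced the Week 105 cut from 5.8% to 2.4% at ρ = 0.7, and from 3.8% to 0.4% at ρ = 0.8. This stands, and is why that term should be the first to go.
- **Age and region.** Their benefit is unproven and may be nil. This stands: the Day 1 score carries the argument.
- **Comparison with the Cox model.** The SAP also fits a Cox model without covariates, and its primary DFS test is an unstratified log-rank test. An unadjusted QOL model is therefore not inconsistent with the rest of the plan. The Cox model shows only that the age and region groupings are already defined.
- **Assumed inputs.** ρ is not in the documents, and QOL is also scheduled at the withdrawal examination, including after relapse where feasible. More follow-up moves the result towards the complete-data cuts, which are slightly larger.
- **Variance components.** The SAP writes both a random-effect and a residual matrix and does not say to which this structure applies. With a random subject effect it would not mean independence. This is a minor point.

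**Conclusion.** The concern holds as a loss of precision, not as an error of validity. Within the assumptions above, leaving out the Day 1 score makes the over-time standard error larger than necessary: including it would cut that SE by 31% at ρ = 0.4, falling to 9% at ρ = 0.8. The direction is certain in that setting for every ρ below 1; the size depends on a correlation the documents do not give. Single-visit gains are smaller, and modest late in the trial. Any benefit from age and region is plausible but cannot be quantified here. The point affects a secondary endpoint of a trial labelled exploratory and leaves DFS and OS untouched. It should still be changed, because the data are collected anyway and the change is cheap.

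**What to change.** In SAP 4.7.2.2, keep the three existing fixed effects and add:

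- the baseline score of the scale being analysed;
- baseline-by-visit interaction;
- age group (60–64, 65–70, ≥71);
- region (Japan; Republic of Korea plus Taiwan, as in the Cox model).

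State that if the model does not converge, baseline-by-visit is removed first, before any change of covariance structure. As a minor safeguard, delete variance components from the fallback list. For any structure other than unstructured, use an empirical variance estimator with a small-sample correction.

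The cost is a few words in the SAP and in the model code, with no new data. The model gains 4 parameters (baseline 1, age 2, region 1), plus 25 while baseline-by-visit is kept. If age and region prove unrelated to QOL, the variance cut shrinks by 1 to 2 points in the simulations above. Late visits need care: the expected number event-free at Week 105 is 60 × 0.20 = 12 on placebo, and 60 × 0.35 = 21 to 60 × 0.40 = 24 on OCV-501.

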4.7.2.3 Performance Status

1) Definition: Performance status (PS) will be scored according to the following criteria.

Grade	ECOG
0	Fully active, able to carry on all pre-disease performance without restriction
1	Restricted in physically strenuous activity but ambulatory and able to carry out work of a light or sedentary nature, e.g, light house work, office work
2	Ambulatory and capable of all self-care but unable to carry out any work activities. Up and about more than 50% of waking hours
3	Capable of only limited self-care, confined to bed or chair more than 50% of waking hours
4	Completely disabled. Cannot carry on any self-care. Totally confined to bed or chair
5	Dead

2) Analysis Set:

FAS, PPS

3) Analysis Method:

- Frequency distributions of PS scores at the baseline and each post-baseline time point (including completion/discontinuation) will be calculated by treatment arm.

- Shift table of PS scores by grade at baseline and the end of trial will be generated by treatment arm.
- PS will be compared at the time of completion or discontinuation based on the improvement factor, which will be defined as follows.

Table 4.7.2.3-2 Improvement Factor	
Improvement factor	Definition
Better	Current PS score < Baseline PS score
No change	Current PS score = Baseline PS score
Worse	Current PS score > Baseline PS score

- To compare the treatment effect in PS improvement factor between treatment arms, Wilcoxon 2-sample test will be carried out.

4.7.3 Reference Efficacy Endpoint

4.7.3.1 DFS until OS cutoff date

1) Definition:

- Observation period: For all subjects, the time from randomization to OS cutoff date
- DFS for reference: The time from randomization until relapse or death from any cause, whichever comes first, by the OS cutoff date
- Event:
Relapse or death from any cause, whichever comes first by the OS cutoff date
- Censoring:
 - If an event has not been observed by the OS cutoff date, the last confirmed non-relapse date will be used as the censoring date.
 - For subjects who have withdrawn from this trial before the OS cutoff date for reasons other than relapse or death, if non-relapse has been confirmed on the withdrawal date, then the withdrawal date will be used as the censoring date. Otherwise, the last confirmed non-relapse date will be used as the censoring date.

2) Analysis Set:

For the judgment of relapse by trial site, DFS will only be evaluated in the FAS.

3) Analysis Method:

The same analysis method will be conducted as for DFS.

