7.1.6.2 Post Treatment for AML

Post treatment (drugs or therapies) for AML after this trial will be surveyed from the last dose of the IMP until the cutoff date for the overall survival for all patients. The start date and regimen of post treatment will be recorded in the medical records and CRF.

If relapse is observed after the post-treatment examination period in any patients who did not show any relapse up to the post-observation period, the date of relapse will also be surveyed up to the cutoff date of OS. The data will be recorded in the medical records and CRF.

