11.3.6 Significance Level and Confidence Interval

Two-sided statistical tests will be conducted at the 5% significance level and 95% confidence interval will be provided.

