3.1.1 Screening Period

The eligible patients will be randomly assigned to one of the following treatment arms at a ratio of 1:1

- OCV-501 arm: 3 mg of OCV-501 (0.4 mL)
- Placebo arm: Placebo (0.4 mL)

The patients will be assigned to either treatment arm via the interactive voice response services (IVRS) or the interactive web response services (IWRS).

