4.12 Determination of Sample Size

The number of AML patients is not very high, and is estimated to be approximately 7000 in Japan⁷. From the fact that in the previous clinical trial (JALSG GML200) in elderly AML patients, it has been forecast that the possible enrollment in Japan is to be at most 70 in one year. Also, from the preliminary trial feasibility survey, it is known that around 50 subjects could be recruited in one year in the Republic of Korea and Taiwan. Through a global trial in Japan, the Republic of Korea and Taiwan, it is considered possible to enroll 120 subjects in one year to assess the efficacy of OCV-501.

Within the limitation of the past experiences with regard to IMP administration, the target sample size will be considered with reference to following publications.^{5,6,7,9} With reference to disease-free survival which has been reported from trials in AML patients 60 years or older who have received the consolidation therapy followed by maintenance therapy, the 2-year DFS rate of placebo arm has been estimated to be around 20%.^{5,6,7}

On the other hand, considering the so-called graft-versus-leukemia (GVL) effect associated with a lower relapse risk after the allogeneic hematopoietic stem cell transplantation, OCV-501 is basically expected to have the same benefits. With reference to the findings of Kurosawa et al,⁹ which have reported a 30% higher 2 or 3-year DFS in elderly AML subjects who have received the allogeneic hematopoietic stem cell transplantation compared with those without transplantation, OCV-501 is expected to have a 15% - 20% higher 2-year DFS. Under the assumption of exponential distribution of DFS time, the hazard ratio (placebo vs. OCV-501) has been set to 0.57 - 0.65, and with a two-sided log-rank test at the 5% significance level, 60 or more subjects in each treatment group can achieve a power of 53% - 75% or more to detect the difference between placebo and OCV-501 groups.

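### The reference DFS counts relapses and deaths after the completion examination, but no later relapse-free date is planned for event-free completers, so the curve beyond 2 years is biased downward and the person-year rates upward.

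*SAP*

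**What the plan says.** SAP 4.7.3.1 defines a reference DFS running from randomization to the OS cutoff. Any relapse (trial-site judgment) or death by then is an event. For subjects without one, "If an event has not been observed by the OS cutoff date, the last confirmed non-relapse date will be used as the censoring date". The methods are those of the primary DFS: log-rank test, Kaplan-Meier, Cox model and, from SAP 4.7.1.1, "the incidence rate over the entire follow-up period will be calculated using the person-year method by treatment arm". SAP 4.13 lists the endpoint as added for reference only.

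The OS cutoff is 728 days after the last subject's first dose (SAP 4.7.2.1), so everyone enrolled earlier has calendar time beyond two years.

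Scheduled relapse assessment ends with the completion examination, about Day 729, which includes a marrow (Protocol 7.1.4.1 and Table 7.1-1). After that, Protocol 7.1.6.1 surveys survival for all patients, and 7.1.6.2 surveys AML post-treatment for all patients. For a patient without earlier relapse in whom one is later observed, "the date of relapse will also be surveyed up to the cutoff date of OS". Neither section asks for a date on which a patient was still relapse-free.

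**The concern.** After the completion examination, events have a planned route into the data and relapse-free time does not. If the last confirmed non-relapse date of an event-free completer is the completion examination, that patient leaves the risk set at about Day 729. A completer who relapses or dies later stays in until the event. Censoring then depends on the outcome, which Kaplan-Meier, the Cox model and the person-year rate all assume it does not.

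At stake is the part of the endpoint that goes beyond the primary DFS. A plotted curve that falls steeply in both arms after two years could be misread as near-universal late relapse. The person-year rates lose event-free time unequally, because the arm with more event-free completers loses more of it.

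**Working it through.** **Inputs.** Two-sided 5% tests (Protocol 11.3.6: "Two-sided statistical tests will be conducted at the 5% significance level and 95% confidence interval will be provided"). Allocation 1:1 (SAP 3.1.1: "The eligible patients will be randomly assigned to one of the following treatment arms at a ratio of 1:1"), 60 per arm. From SAP 4.12: "the 2-year DFS rate of placebo arm has been estimated to be around 20" per cent; "OCV-501 is expected to have a 15% - 20% higher 2-year DFS", hence 35-40%; exponential DFS times; "the hazard ratio (placebo vs. OCV-501) has been set to 0.57 - 0.65"; enrollment of 120 in one year. Two-year accrual is my added assumption. The scheduled duration, September 2013 through December 2017, is 52 months; less about 24 months of follow-up after the last entry, it leaves room for up to about 28.

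**The plan's own figure first.** The documents give no figure for the reference DFS, so I check the DFS power. HR = ln(0.35)/ln(0.20) = 0.652, or ln(0.40)/ln(0.20) = 0.569. Two-year events = 60×0.80 + 60×0.65 = 87, or 48 + 36 = 84. Schoenfeld power = Φ(√events × |ln HR|/2 − 1.96):
- 87 events: Φ(9.33×0.427/2 − 1.96) = 51%, against 53% stated.
- 84 events: Φ(9.17×0.563/2 − 1.96) = 73%, against 75% stated.

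Both are within 2 points, so the inputs are read correctly.

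**True values past 2 years, if the hazard stays constant.** Hazard = −ln(S₂)/2: 0.80/year on placebo, 0.525 (35%) or 0.458 (40%) on OCV-501. S(2.5) = S₂^1.25: 0.20^1.25 = 13%; 0.35^1.25 = 27%; 0.40^1.25 = 32%.

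**Simulation.** 120 patients per trial, uniform entry, no withdrawals, events kept to the OS cutoff. Event-free patients are censored at completion (no later date recorded) or at the OS cutoff (date surveyed). With one-year accrual about 3.7 placebo and 4.6 OCV-501 events fall after completion; with two-year accrual about 6 and 8.

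Kaplan-Meier DFS at 2.5 years:

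| Accrual | Later relapse-free dates | Placebo (true 13%) | OCV-501 (true 27-32%) |
|---|---|---|---|
| 1 year | none | 4% | 8-9% |
| 1 year | half | about 11% | 23-27% |
| 2 years | none | 8% | 16-19% |

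With all dates surveyed, the estimates match the true values to within about 0.005.

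**Person-year rate over the whole period (no date vs surveyed date).**
- Placebo: 0.863 vs 0.820 (+5%) up to 0.881 vs 0.826 (+7%).
- OCV-501: 0.586 vs 0.536 (+9%) up to 0.535 vs 0.464 (+15%).

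**Comparison between arms (no date vs surveyed date).**
- Whole-period HR: 0.677 vs 0.662 and 0.680 vs 0.656 (35%, 1- and 2-year accrual); 0.593 vs 0.570 and 0.595 vs 0.564 (40%).
- Power of this reference test falls by about 4-9 points.
- Rejection under the null: 5.7% vs 5.2% in 600 trials, where the simulation standard error is √(0.05×0.95/600) = 0.9 points.

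**What does not move.** No completer is censored before about Day 729, so the 2-year rate stays at 0.20 and 0.35/0.40. The medians, ln 2/hazard = 0.86 years on placebo and at most 1.51 on OCV-501, lie well before that.

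**The case against.** The strongest reply is that SAP 4.7.3.1 does not name the completion examination. It refers to the last confirmed non-relapse date, over a period running to the OS cutoff and by trial-site judgment. A site reporting no relapse may supply a dated status, and Protocol 7.1.6.1 has reasons for censoring recorded. The eCRF is not among the documents and may hold a suitable field.

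This stands as a limit on size. With one-year accrual and 25%, 50% or 80% of later dates recorded, placebo at 2.5 years is about 8%, 10-11% and 12%; OCV-501 under the 35% assumption is about 18%, 23% and 26%. It does not remove the defect: neither document requires the date, so the curve would depend on uneven site practice.

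Three stronger readings are tempting and not supported:

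- *That both curves must fall to zero whatever the drug does.* That happens only if no later date is recorded.
- *That a late treatment difference is erased.* No post-2-year hazard ratio is planned as such, and the 3-month hazard ratios are run only if proportionality fails. With 3.7 and 4.6 late events, SE(log HR) = √(1/3.7 + 1/4.6) = 0.70, so a late HR of 0.65 would have a 95% interval of about 0.17 to 2.6 even with correct censoring.
- *That the main result is biased.* The primary DFS stops at each subject's completion or discontinuation (SAP 4.7.1.1), and no decision is tied to the reference endpoint.

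The constant hazard is also open to challenge. The cited studies in Protocol 3.2 imply lower hazards in year 3: ln(10/5) = 0.69, ln(32/27) = 0.17 and ln(20/18) = 0.11 per year. A lower hazard changes the event counts and sizes, not the direction.

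**Conclusion.** The concern holds for the reference endpoint alone. Events after completion are counted to the OS cutoff, while no relapse-free date is planned beyond about Day 729 for completers who stay event-free. Followed as stated, and without incidental later dates, the rule biases the post-2-year curve downward in both arms and inflates the whole-period person-year rates, more on OCV-501 than on placebo. The effect on the whole-period hazard ratio is small. Any late hazard ratio rests on about 4 to 8 events per arm and is uninformative either way.

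The sizes assume the SAP's planning rates, a constant hazard past two years, uniform entry over one or two years, and no withdrawals. Early withdrawals can raise the same asymmetry before two years; that is a separate matter and is not sized here, since no dropout rate is given. Because the endpoint is labelled reference, this is worth correcting but does not threaten the trial's main conclusion.

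**What to change.** 1. In the outcome survey already made to the OS cutoff (Protocol 7.1.6), add one field for every subject without relapse: date last known free of relapse.
2. In SAP 4.7.3.1, state that completers without an event are censored at that date.
3. If these dates cannot be collected for most completers, end the reference analysis at the completion examination for all subjects, counting neither relapses nor deaths after it. Individual missing dates should not cancel the extended analysis.
4. Do not treat the absence of recorded AML post-treatment as proof of no relapse. Use it, if at all, in a labelled sensitivity analysis.

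The cost is a sentence or two in the SAP and a small protocol and CRF amendment for one date field, with no added visit or test. The downside is that a surveyed relapse-free date is less exact than one from a study examination.
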